## Evaluating an Eating Disorder Prevention Program for Young Women With Type 1 Diabetes

NCT05264376

January 31, 2024

Statistical Analysis Plan

For all outcomes except TIR we fit a linear mixed effect model where we regressed the outcome onto the pretest score for the outcome, treatment group (coded as treatment group 1, 2, 3, 4, or 5 or 0 for control), assessment (coded 0 for post-test and 1 for follow-up), and the interaction of condition (coded 0 for control or 1 for treatment) and assessment. Using treatment group instead of condition as a main effect enabled us to control for the partially nested design, where observations were nested within participants for the control condition and where observations were nested within participants nested within groups for the treatment condition. We included treatment group as a fixed effect rather than a random effect because the number of groups (n = 5) and the number of participants per group were small (n = 6). To control for repeated measurements for each participant we included a random intercept. Models tested for condition differences at post-test and 3 month follow-up. Because TIR was measured only at pretest and 3 month follow-up, we fit a multiple regression model where we regressed TIR at 3-month follow-up onto the pretest TIR score and treatment group. For all models, we examined modeling assumptions and transformed data as necessary. We square root transformed eating disorder symptoms to meet normality and homogeneity of variance assumptions. Missingness at pretest ranged from 0% to 11% for TIR; at posttest ranged from 11% for EDS to 15% for TII, BD, DD, and QOL; and at 3month follow-up ranged from 7% for EDS to 18% for TIR. Missingness was assumed to be missing at random and full information maximum likelihood was used to handle missing data, consistent with an intent-to-treat approach. Models were fit in R using the lavaan package.

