1. PURPOSE OF THE STUDY

a. Brief Summary

This study aims to test the effectiveness of an evidence-based eating-disorder prevention program specifically targeted for individuals with Type 1 Diabetes (T1D) compared to an educational control group. The Diabetes Body Project (DBP), is an adaptation of the Body Project which is the only eating disorder prevention program to have repeatedly produced effects when evaluated by independent researchers, produced stronger effects than credible alternative interventions, and affected objective outcomes. DBP has been adapted slightly for individuals with T1D who are at ultra-high risk for eating disorders. The study aims to test the effectiveness of the DBP of reducing body image concerns and reducing eating pathology and improving glycemic control.

b. Objectives

Aim 1 is to test the hypothesis that participants who complete the Diabetes Body Project will show significantly greater improvements in glucose control (HbA1c and Time in Range [TIR]), the primary outcomes, as well as reductions in diabetes distress, illness perceptions, and quality of life (secondary outcomes) over follow-up than control participants who view educational lectures of diabetes management and EDs. Although HbA1c is the most common measure of long-term blood glucose management (ADA, 2018), with the advent of continuous glucose monitoring (CGM), the ability to classify sensor glucose levels into various ranges has been feasible. Time in Range (TIR), which reflects the amount of time an individual had glucose values between 70 and 180 mg/dL, has shown a robust inverse association with development of diabetic retinopathy and microalbuminuria (Beck et al., 2019). As of July 2022, we are making the CGM optional, this will decrease our power to detect changes in TIR.

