2) the 9-item Body Dissatisfaction Scale (Berscheid et al., 2973) which assesses dissatisfaction with various body parts

3) the 16-item Diabetes Eating Problem Survey-Revised (Markowitz et al, 2010)

4) the 28-item Type 1 Diabetes Distress Scale (Fisher et al., 2015) which assesses distress related to diabetes

5) the 5-item World Health Organization Well-Being Index (deWit et al., 2007) that assess health related quality of life

6) Negative affect will be assessed with the sadness, guilt, and fear/anxiety subscales (totaling 20 items) from the Positive Affect and Negative Affect Scale-Revised (PANAS-X; Watson & Clark, 1992)

7) 10-item Dutch Restrained Eating Scale (van Strien et al., 1986) that measures dieting behaviors.

At the baseline assessment, participants will also complete an Eating Disorder Diagnostic Interview (EDDI) over the phone. The EDDI can take between 30 to 60 minutes to complete depending on the number of behaviors endorsed by the participant. The EDDI will be administered by a trained research assistant. At baseline, participants will also be asked to report their A1Cs. We will only ask for self-reported A1Cs.

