We selected a T1D management/ED psychoeducational comparison condition previously tested (Olmsted et al., 2002) to control for expectancy effects and demand characteristics. To match the Diabetes Body Project, the educational lectures by [name] will be delivered in 6 1-hour blocks. Topics include basic information about the various eating disorders, complications of ED behaviors, diabetes and body image, effects of dieting on blood glucose, and the risk of complications. Strategies to develop a healthy relationship with food, how to overcome binge eating and purging behaviors (including intentional insulin omission), and how to improve body image are also discussed. If participants are randomized to the Diabetes Body Project, they will meet in groups of 6 individuals co-led by a peer educator with T1D and a clinician. Groups will meet once a week virtually for an hour, for six weeks. Each week involves homework that participants are asked to complete before the next session. If participants are assigned to the Education intervention, they will be asked to watch one-hour of videos including information about diabetes management and eating disorders each week for six weeks. Post-Test:

After the six weeks of either Diabetes Body Project or the educational control, participants will be asked to complete the same questionnaires that they assessed at baseline and the EDDI.

3-Month Follow-up:

At 3-month follow-up, participants will again complete the questionnaires and the EDDI, but will also wear the continuous glucose monitor (either the one they already have or the

Libre 2 provided by the research staff) and be asked to self-report A1c. After the 3-month follow-up, participants have completed all study responsibilities.

b. Procedure Risks

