participants will have completed all necessary tasks until the 3-month follow-up where they will complete the same tasks as the baseline assessment and where the CGM for two weeks. While the groups are running, data analysis on baseline data will begin. Once we have complete data for posttest and 3-month follow-up, we will conduct data analysis on the outcome measures.

5. **RISKS**

a. Potential Risks

i. Investigational devices

None

ii. Investigational drugs

None

iii. Commercially available drugs, biologics, reagents or chemicals

There are no risks of commercially available drugs, reagents, or chemicals as none will be used.

iv. Procedures

Data Collection: Self-reported survey will be kept confidential and collected online via secure RedCap database system. The diagnostic interviews will require phone numbers as they will be conducted over the phone, but the interview forms will only be labeled with the participant ID number. All stored and collected interview data will not include names or phone numbers. There are no known psychological risks to subjects completing self-report subjective rating scales or participating in the intervention sessions. However, the survey and intervention may contain items or questions that make the subjects feel uncomfortable in that they ask about their physical and psychological health and feelings/emotions. Subjects will be informed that any items on questionnaires or topics discussed in the intervention modules that produce these effects may be skipped or ignored.

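### HbA1c, one of the two primary outcomes, falls under a mixed model that cannot be fitted to its two-point schedule, and the SAP gives no other HbA1c analysis

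*SAP*

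**What the plan says.** Protocol section 1b sets Aim 1 as a test of "significantly greater improvements in glucose control (HbA1c and Time in Range [TIR]), the primary outcomes".

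Protocol section 2a fixes when HbA1c is obtained:

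- Baseline: "At baseline, participants will also be asked to report their A1Cs". This is listed apart from the seven questionnaires and the diagnostic interview (EDDI).
- Post-test: "participants will be asked to complete the same questionnaires that they assessed at baseline and the EDDI". HbA1c is not mentioned.
- 3-month follow-up: besides the questionnaires and EDDI, participants wear the glucose monitor and will "be asked to self-report A1c".

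Section 4m agrees. After the post-test, "participants will have completed all necessary tasks until the 3-month follow-up where they will complete the same tasks as the baseline assessment".

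The SAP has one general rule and one exception. The rule is "For all outcomes except TIR we fit a linear mixed effect model", with pretest score, treatment group (0 for control, 1 to 5 for the intervention groups), assessment (0 post-test, 1 follow-up), condition by assessment, and a participant random intercept. The exception is justified by "Because TIR was measured only at pretest and 3 month follow-up", and for that outcome "we regressed TIR at 3-month follow-up onto the pretest TIR score and treatment group". HbA1c does not appear anywhere in the SAP.

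**The concern.** The SAP's reason for exempting TIR applies equally to HbA1c, but the exemption covers TIR alone. Read literally, the general rule sends HbA1c to a repeated-measures model for two post-baseline visits when the protocol schedules only one. If the rule is not meant to include HbA1c, then no analysis of it is stated at all.

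HbA1c is half of the primary objective. Protocol section 1b also concedes that making the glucose monitor optional reduces power for TIR, so more weight falls on HbA1c. As things stand, a reader cannot tell which model, which condition contrast or how much missing data lies behind any HbA1c result. That result therefore cannot be checked against a plan.

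**Working it through.** The documents give no power or precision figure on this point, so there is none to reproduce. The check is whether the stated model can be estimated.

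**Inputs**

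- Five intervention groups of 6 (SAP).
- Control-arm size: not in the SAP. Taken as 30, from planned enrolment of 60 (protocol section 4a) minus 5 x 6, and varied from 20 to 40.
- Treatment group read as a categorical fixed effect, giving five indicators with control as reference.
- HbA1c at baseline and 3 months only (protocol section 2a).

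**Step 1: the SAP model.** For participant i at assessment A (0 or 1), with group indicators G1 to G5 and condition C:

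Y = b0 + b1 Pre + (g1 G1 + ... + g5 G5) + d A + h (C x A) + u + e

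Fixed-effect columns: 1 + 1 + 5 + 1 + 1 = 9. With both visits and 30 controls there are 120 rows and the rank is 9 of 9. The two variance components are separable, so the model works for outcomes measured at both visits.

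**Step 2: the same model with 3-month rows only.** Now A = 1 in every row, and C = G1 + ... + G5 always. Substituting:

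Y = (b0 + d) + b1 Pre + (g1 + h) G1 + ... + (g5 + h) G5 + (u + e)

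- d appears only in b0 + d, so the assessment column duplicates the intercept.
- h appears only in g1 + h to g5 + h, so the interaction column is the sum of the group indicators.
- u appears only in u + e, so only the total variance can be estimated.

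Two of the 9 columns are redundant: 60 rows, rank 9 - 2 = 7. The assessment effect, the interaction, the post-test condition difference and the variance split cannot be estimated. The 3-month condition difference, the mean of (g1 + h) to (g5 + h), can be estimated once the redundant terms are removed.

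**Step 3: the TIR-type regression.** Intercept, pretest and five group indicators give 7 columns with rank 7, so it is identified. Adding condition beside the group indicators gives 8 columns with rank 7, so condition cannot be added as a separate term.

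**Step 4: sensitivity.** The ranks (9 of 9, 7 of 9, 7 of 7, 7 of 8) were the same for control arms of 20, 25, 30, 35 and 40, with groups of 6 and with groups of 5, 6, 6, 5 and 6: ten cases in all.

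**Step 5: why the contrast must be stated.** Ignoring the covariate and missing data, in residual SD units with 30 controls:

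- Average of five groups against control: sqrt(1/30 + 1/30) = 0.258.
- One group against control: sqrt(1/6 + 1/30) = 0.447.

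For the average contrast, 20 controls give sqrt(1/20 + 1/30) = 0.289 and 40 give sqrt(1/40 + 1/30) = 0.242.

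**Step 6: can the SAP's missing-data statements rescue the model?** Under the protocol schedule, HbA1c at post-test would be 100% missing, while the SAP's stated post-test range is 11% to 15%. Full information maximum likelihood does not help, because with no post-test HbA1c in anyone there is nothing from which to estimate a post-test effect.

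**The case against.** The strongest reply is that the SAP is a past-tense report, so its general rule may cover only the outcomes actually analysed. It names several outcomes by abbreviation and singles out TIR as lacking a post-test value. On that reading the model is identified for every outcome it was applied to, and the real defect is that HbA1c is absent. This reading is possible and the documents cannot exclude it. It does not help the plan, because a primary outcome then has no stated analysis.

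Second, the repair is obvious: drop the redundant terms and the TIR regression remains. This is true, and the 3-month contrast is recoverable. But the SAP does not say this was done, and it names no condition contrast for that regression. The missing contrast affects TIR equally.

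Third, no passage states outright that HbA1c was not collected at post-test. That is correct. It is the plain reading of section 2a, which presents HbA1c and glucose monitoring together as additions at 3 months. Section 4m alone would not settle it.

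Fourth, the standard errors rest on an assumed control arm and complete data. With 18% missing, the SAP's 3-month figure for TIR, 0.258 would become sqrt(2/24.6) = 0.285, where 24.6 = 30 x 0.82. This stands as a caution on those figures. The rank result does not depend on them.

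**Conclusion.** The concern holds. For one of two primary outcomes, the only rule that could apply cannot be fitted as written (rank 7 of 9, random intercept not separable from the residual), and no alternative is given. The finding rests on the protocol's HbA1c schedule having been followed and on treatment group entering as five indicators; it does not depend on the arm sizes tried. It does not show that HbA1c was omitted or selectively reported, only that no workable analysis of it is specified. This needs correcting before any HbA1c result is presented as a planned primary analysis.

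**What to change.** - State in the SAP whether HbA1c was collected at post-test and whether it was analysed. If it was collected at post-test, or was not analysed, say so and justify the departure from the protocol.
- If it was collected as the protocol schedules, extend the exception to read: all outcomes except TIR and HbA1c. Regress 3-month HbA1c on pretest HbA1c and treatment group, as for TIR.
- Define the condition effect as the average of the five group coefficients against control. Equal weights match the SAP's groups of 6. Do not add a condition term beside the group indicators.
- Use the same missing-data handling as for the other outcomes, and give HbA1c missingness by arm.
- Label the specification as made after data collection, and report the result as primary whatever its direction.

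The cost is one or two SAP sentences and one regression, provided the planned self-reports were obtained. The documents do not say how many were.

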For the last part of the baseline assessment, Glucose monitoring data will be collected via glucose monitors that are already in use, among participants already using these devices at the time of enrollment, with data being shared by the participant with the research team via secure online portals created and run by their corresponding device company. For participants who are not already using glucose monitors at the time of enrollment, they will be given the option of us sending them one. If they agree to wearing a CGM then a Libre 2 glucose monitor devices will be provided by study staff, as well as training on use following FDA-approved self-start guides that are available online. See section 16 for the Libre 2 informational brochure. However, if a participant does no already have a CGM and does not want to wear one, then we will not send them one. This means they will not receive the \$25 at baseline and at the 3-month follow-up that is set aside for the two-week CGM information. They will be made aware of this when they decide not to wear the Libre2. The CGM is invasive, but it is a quick process that participants do at home. It is quick and often painless. Also in section 16 is a link to a video illustrating how to apply the sensor. Research staff will also provide support throughout use, and will be used to collect 2 weeks of data at each time point.

Prevention Program:

After baseline assessments are completed, participants will be randomized to either the Diabetes Body Project groups or the educational control.

Randomization:

We will use a random number generator to determine if participants will be in Diabetes Body Project or the educational control. If an even number is generated, the participant will be assigned DBP. If an odd number is generated, the participant will be assigned to educational control. As there is a 50% chance the number will be either even or odd, there is a 50% chance that someone will be assigned either to DBP or the educational control. It is only after the baseline assessment that individuals will be randomized. This will prevent the assessor at baseline from being influenced by which group the participant will be in. The assessor completing the EDDI at post-test and 3-month follow-up will be blind to the participant's condition.

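### Should the TIR model borrow self-reported HbA1c to make up for participants with no CGM data?

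*SAP*

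**What the plan says.** The SAP analyses TIR apart from the other outcomes because it was measured only at pretest and 3 months: "we regressed TIR at 3-month follow-up onto the pretest TIR score and treatment group". On missing data it says "Missingness was assumed to be missing at random and full information maximum likelihood was used to handle missing data". TIR is missing for 11% at pretest. Across outcomes, missingness "at 3month follow-up ranged from 7% for EDS to 18% for TIR". No auxiliary variable is named, and HbA1c is not mentioned anywhere in the SAP.

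The Protocol (section 1b, Objectives) names HbA1c and TIR as the primary outcomes and concedes the cost of its own change: "As of July 2022, we are making the CGM optional, this will decrease our power to detect changes in TIR". In section 2a the CGM offer is part of the baseline assessment, and "if a participant does no already have a CGM and does not want to wear one, then we will not send them one". Allocation comes later: "After baseline assessments are completed, participants will be randomized to either the Diabetes Body Project groups or the educational control". HbA1c is requested whether or not a CGM is worn. The baseline text reads "At baseline, participants will also be asked to report their A1Cs. We will only ask for self-reported A1Cs", and the 3-month text repeats the request.

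**The concern.** FIML draws only on variables that are in the model. With pretest TIR, 3-month TIR and group as the only variables, someone with neither TIR value carries no weight. The loss is in fact a little wider. If everyone missing pretest TIR also misses it at 3 months, those with pretest TIR alone add nothing to the treatment coefficient either. In simulation the FIML and complete-case standard errors were then identical.

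HbA1c is the measured variable closest to TIR, it is requested twice from everyone, and it can enter FIML as a saturated correlate without changing the estimand. On a first reading the plan leaves precision unused on a primary outcome whose power it already knows is reduced. It also rests on a missing-at-random assumption that HbA1c might make more believable. The SAP gives missingness overall and not by arm, so a reader cannot judge that assumption.

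**Working it through.** The plan has no power calculation or standard error to reproduce, so the check sizes the possible gain.

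**1. Counts behind the percentages.** The SAP's rounded figures of 11%, 15%, 7% and 18% were tried against every N from 40 to 70. Only two fit:

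- N = 55: 6, 8, 4 and 10 missing (10.9%, 14.5%, 7.3%, 18.2%)
- N = 61: 7, 9, 4 and 11 missing (11.5%, 14.8%, 6.6%, 18.0%)

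The planned 60 does not fit (6/60 = 10.0%, 7/60 = 11.7%). In both solutions the pretest TIR count plus the lowest 3-month count equals the 3-month TIR count: 6 + 4 = 10 and 7 + 4 = 11. That suggests 6 or 7 people without TIR throughout, plus 4 lost to the 3-month visit altogether. The SAP does not report the overlap, so this is an inference. The number lacking TIR at both times is at most 11%.

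**2. Closed form.** Let *m* be the fraction lacking 3-month TIR among those with 3-month HbA1c, and *r* the correlation of the two given pretest TIR and group. The ratio of variances, with and without the auxiliary, is 1 − r²m. If the 7% lost to the visit also lack HbA1c, m = 1 − 0.82/0.93 = 0.118. If everyone supplies HbA1c, m = 0.18.

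| r (assumed) | SE change, m = 0.118 | SE change, m = 0.18 |
|---|---|---|
| 0.3 | √0.989: −0.5% | √0.984: −0.8% |
| 0.5 | √0.970: −1.5% | √0.955: −2.3% |
| 0.7 | √0.942: −2.9% | √0.912: −4.5% |

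**3. Detectable difference.** Assume N = 55, 18% missing, equal arms, pre-post correlation 0.7 (residual variance 1 − 0.49 = 0.51), two-sided 5% and 80% power. Then 2.802 × √(0.51 × 2/22.55) = 0.596 SD. With m = 0.118 this becomes 0.596 × √0.970 = 0.587 SD at r = 0.5 and 0.596 × √0.942 = 0.578 SD at r = 0.7.

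**4. Simulation of the SAP model** (six-level group, FIML by EM, with and without both HbA1c values):

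- N = 60, 4,000 replicates, pre-post correlation 0.7, 7 decliners and 4 lost to the visit. The SE is 0.188 with no missing TIR and 0.210 under the SAP model. With HbA1c it is 0.209, 0.207 and 0.204 for r = 0.3, 0.5 and 0.7, a fall of 0.5%, 1.4% and 2.9%. Power for a true effect of 0.50 SD goes from 66.2% to 66.6%, 67.5% and 69.0%.
- In that scenario missing TIR costs 1 − (0.188/0.210)² = 19.9% of the information, or 11.9 of 60 participants. At r = 0.5 the auxiliaries recover 12% of it, worth 0.12 × 11.9 = 1.4 participants.
- N = 55, overlapping missingness, visit loss also losing HbA1c, 500 replicates, pre-post correlation 0.6 or 0.8. The SE falls 2.3% to 2.4% at r = 0.5 and 3.7% to 3.8% at r = 0.7.
- A separate paired run at N = 55 gave SE ratios of 1.006, 0.984 and 0.975 for r = 0.3, 0.5 and 0.7. If half the decliners also lack HbA1c, they were 1.001, 0.987 and 0.986.

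**5. Bias.** Declining happens before allocation. With declining driven by baseline control (20% v 2%), the SAP model returned 0.500 for a true 0.500. To produce bias, one must suppose that controls with poor 3-month HbA1c skip TIR (30% v 2%), for which the documents give no support. The estimate is then 0.465 (r = 0.5) or 0.451 (r = 0.7), which is 0.035/0.210 = 0.17 to 0.049/0.210 = 0.23 standard errors low. HbA1c repairs this (0.497, 0.496) only if those who skip still report HbA1c. If they do not, it stays at 0.466 or 0.452. Step 1 points to visit loss as the main post-randomization route, which is the case without repair.

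**The case for a change.** The best case for acting is that TIR is a primary outcome, has the highest reported missingness at pretest and at 3 months, and sits beside a close proxy that costs a few lines of code to add. Under kinder assumptions the gain is larger. If the pretest and 3-month losses fall on different people, r is 0.8 and HbA1c is complete, simulation cut the SE by up to 9.7%. HbA1c is also the natural variable for making missing at random more plausible.

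Some of this stands. Adding the two values is legitimate, and harmless in simulation (SE at most 0.2% higher when they cannot help). Showing TIR missingness by arm, with the number lacking 3-month TIR who do have HbA1c, would help a reader. But that is a reporting request and corrects no error in the plan.

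The favourable case is doubtful on three counts. The counts in step 1 fit overlapping losses better than separate ones. HbA1c is self-report only, the Protocol gives no date window for the value, and eligibility asks only for a diabetes care visit in the past year. A figure given at 3 months could therefore predate the intervention, which favours the low end of r. Finally, the data are requested, but the documents do not show how completely they were obtained.

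The SAP also leaves unsaid whether lavaan treated pretest TIR as fixed, which would drop people missing it. If those people lack 3-month TIR as well, the setting makes no difference to the treatment estimate.

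**Conclusion.** No change is needed. The TIR model is a standard baseline-adjusted regression with a stated missing-data method and assumption. Leaving out an auxiliary variable is a reasonable choice in a sample of about 55 to 61 with five group terms. The gain forgone is about 0% to 3% of the standard error in closed form, and under 4% in simulation, for TIR-HbA1c correlations of 0.3 to 0.7. It shrinks towards nothing if those lacking TIR also lack HbA1c. No bias follows from declining a CGM before randomization, and the loss that could bias the contrast is largely the kind HbA1c could not repair.

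The Protocol already discloses the optional CGM and its cost in power, and the SAP already reports the missing fractions. Because the SAP reports observed missingness, an HbA1c-augmented model could now only be a labelled sensitivity analysis, which the analysts may run or decline. These sizes rest on assumed correlations (0.3 to 0.7 between TIR and HbA1c, 0.6 to 0.8 pre to post) and on the inferred overlap of missing values, none of which the documents give.

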(i) All subjects will be enrolled at Stanford. We expect to enroll 60 participants. (ii) N/A (iii) Participants are female-identifying individuals between 15-30 years old with a Type 1 Diabetes diagnosis of at least six months. We are recruiting 15-30 females with T1D as they are at an elevated risk of eating disorders due to T1D and their gender. As this is the first test of the Diabetes Body Project, recruiting a sample that will most likely benefit from it is important in testing its effectiveness.

b. Age, Gender, and Ethnic Background

All participants will be female-identifying 15–30-year-olds. All ethnicities will be recruited and included.

c. Vulnerable Populations

Participants aged 15-17 years-old may be considered potentially vulnerable subjects as they are not yet adults. Adolescents (aged 15-17), especially female adolescents, are at an elevated risk of eating disorder onset and serve to benefit from the eating disorder prevention program. Parental consent will be required before adolescents' assent to partake in the study. Parents will be informed of all tasks the adolescents will be asked to complete (surveys, glucose monitoring, diagnostic interview, and treatment group).

d. Rationale for Exclusion of Certain Populations

Women, minorities, and adolescents (aged 15-17) are included in the study. Children younger than 15 are not included in the study as they are less likely to have an eating disorder or body dissatisfaction. Additionally, the Diabetes Body Project was designed for older adolescents.

e. Stanford Populations

None.

f. Healthy Volunteers

None.

g. Recruitment Details

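### Time in Range: full maximum likelihood with seven coefficients and no small-sample correction makes standard errors about 7–8% too small, so a nominal 5% test runs at about 7–8%

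*SAP*

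**What the plan says.** Protocol section 1b (Objectives) names "improvements in glucose control (HbA1c and Time in Range [TIR]), the primary outcomes". Section 4a (Planned Enrollment) says "We expect to enroll 60 participants".

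The SAP is a single section. For TIR, "we regressed TIR at 3-month follow-up onto the pretest TIR score and treatment group". Treatment group is coded 0 for control and 1 to 5 for the five intervention groups, and is entered as a fixed effect. On missing data it reports "Missingness at pretest ranged from 0% to 11% for TIR" and, for the last assessment, "at 3month follow-up ranged from 7% for EDS to 18% for TIR". On estimation it says "full information maximum likelihood was used to handle missing data, consistent with an intent-to-treat approach. Models were fit in R using the lavaan package".

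On inference it says only "Models tested for condition differences at post-test and 3 month follow-up". It does not give alpha, a reference distribution, a degrees-of-freedom method, the number analysed, or how the five group coefficients become one condition effect for TIR.

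**The concern.** Maximum likelihood estimates the residual variance as RSS/n. The unbiased estimate is RSS/(n−p), where p is the number of mean parameters. The difference is trivial when n is large relative to p. Here the five group dummies bring p to 7, against fewer than 50 observed outcomes. If the resulting Wald statistic is also referred to the normal distribution, a second and smaller inflation is added, because a t distribution on about 40 degrees of freedom has heavier tails.

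Both errors act in the same direction: intervals too narrow and p-values too small on a primary outcome. The Protocol makes the result consequential. Section 2f offers the programme to controls if it proves significantly better, and section 1b looks to the results to support a larger trial. Section 1b also concedes that making the glucose monitor optional reduces power for TIR, so a borderline result is plausible.

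**Working it through.** The documents state no type I error or power figure, so there is nothing of the plan's own to reproduce.

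**Inputs from the documents**
- Planned N = 60 (Protocol 4a).
- TIR missing: 11% at pretest, 18% at 3 months (SAP).
- TIR model: intercept + pretest + 5 group dummies, so p = 7 (SAP).

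**Assumptions**
- Two-sided alpha of 5%.
- Normal reference for the ML Wald test; a t reference is shown as the milder case.
- One-degree-of-freedom contrast: mean of the five group coefficients against control.
- Normal errors and no between-group variance.
- Number analysed. 60 × 0.82 = 49.2, so n ≈ 49. The SAP's rounded missingness figures (7%, 11%, 15%, 18%) cannot all arise from N = 60, since 6/60 = 10% and 7/60 = 11.7%. N = 55 reproduces all four, and so does N = 61. For N = 55, 55 × 0.82 = 45.1, so n ≈ 45.

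**Step 1: standard error.** The ratio of the ML to the unbiased standard error is √((n−p)/n).
- n = 49: √(42/49) = 0.926, or 7.4% too small.
- n = 45: √(38/45) = 0.919, or 8.1% too small.

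**Step 2: true size, normal reference.** Size = P(|t₍ₙ₋ₚ₎| > 1.96·√((n−p)/n)).
- n = 49: P(|t₄₂| > 1.815) = 7.7%; coverage 92.3%.
- n = 45: P(|t₃₈| > 1.801) = 8.0%; coverage 92.0%.

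**Step 3: the two sources separated**

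| | n = 49 | n = 45 |
|---|---|---|
| ML standard error, normal reference | 7.7% | 8.0% |
| ML standard error, t reference | 6.9% | 7.1% |
| Unbiased standard error, normal reference | 5.7% | 5.7% |
| Unbiased standard error, t reference | 5.0% | 5.0% |

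The divisor is the larger source, but both must be corrected.

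**Step 4: which results change.** The corrected test needs an ML z above t₀.₉₇₅/√((n−p)/n).
- n = 49: 2.018/0.926 = 2.180, an ML p-value of 0.029.
- n = 45: 2.024/0.919 = 2.203, an ML p-value of 0.028.

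Results reported with p between about 0.03 and 0.05 would lose significance. Dividing these thresholds by 1.96 gives the interval width ratio: 1.112 and 1.124.

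**Step 5: check with missing pretest values.** The closed form treats the data as complete, whereas FIML may keep participants without a pretest. FIML was therefore simulated with 11% of pretest and 18% of follow-up TIR missing completely at random, using observed-information standard errors and a normal reference. The pretest–follow-up correlation is an assumption.

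| Correlation | N = 60 | N = 55 |
|---|---|---|
| 0.5 | 8.1% | 7.6% |
| 0.6 | 7.9% | 8.2% |
| 0.7 | 8.0% | 8.4% |

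There were 12,000 runs per setting at 0.6 and 8,000 at 0.5 and 0.7 (Monte Carlo error up to about 0.3 points). The closed form is confirmed and does not overstate the problem.

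**Step 6: repeated outcomes.** The mixed model has 9 mean parameters (the 7 above plus assessment and condition-by-assessment). The simulation assumed within-person correlation 0.3, 0.6 or 0.8, 15% missing at post-test, 11% or 18% at follow-up, and N = 60 or 55. ML with a normal reference gave 6.6–7.5% for the condition contrasts and 6.0–6.7% for the interaction. REML with Satterthwaite degrees of freedom, run on the 18% settings, gave 4.8–5.4%.

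**The case against.** The strongest reply is that the SAP is a one-paragraph summary. It names an estimator and a package but not its test statistics, so silence about a correction does not prove that none was used. Alpha, the reference distribution, the contrast and the number analysed are all unstated, and the answer depends on them. That stands as a limit on certainty, but it does not rescue the plan. The milder t reference still leaves 6.9–7.1%. The one-degree-of-freedom contrast is the milder reading of the group factor: a five-degree-of-freedom joint Wald test would run at 11.5% (n = 49) or 12.3% (n = 45). A model with condition only (p = 3) would run at about 6.4–6.5%, but the SAP does not describe that model.

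A second objection is that 60 does not fit the reported missingness. That is right, and 55 fits; the move from 60 to 55 makes the result slightly worse.

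A third is that the remedy restores 5% only without between-group variance. That also stands. With fixed group dummies, variation between groups is left out of the error term. At n = 45, assumed intraclass correlations of 0.05 and 0.10 would leave the corrected test at about 6.3% and 7.8%. This is a separate problem, which the correction neither causes nor cures.

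Finally, the effect is 2 to 3 percentage points in what the Protocol calls a pilot, and FIML under missing at random is an accepted method. Both are true. The objection here is to the uncorrected variance and reference, not to the missing-at-random approach.

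**Conclusion.** The concern holds. As written, the TIR analysis gives standard errors 7.4% to 8.1% too small. A nominal two-sided 5% test then has a true size of 7.7% to 8.0% with a normal reference, or 6.9% to 7.1% with a t reference. These figures rest on an unstated alpha, on a single contrast of the five groups against control, and on 49 or 45 observed outcomes. The direction does not depend on which of those readings is taken. The repeated outcomes share the fault to a smaller degree. Estimates are unbiased by it. What is at risk is the status of a primary-outcome result with a reported p between about 0.03 and 0.05, and the coverage of every interval.

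**What to change.** - Analyse TIR with residual variance RSS/(n−p) and a t reference on n−p degrees of freedom.
- Do the same for any outcome with a single post-baseline measurement. This applies to the other primary outcome: Protocol section 2a collects A1c by self-report at baseline and at 3 months ("Libre 2 provided by the research staff) and be asked to self-report A1c") and lists none at post-test.
- Fit the repeated outcomes by REML with Satterthwaite or Kenward-Roger degrees of freedom.
- Handle missing pretest values by a missing-at-random method with small-sample degrees of freedom; multiple imputation is one option.
- State alpha, the reference distribution, the number analysed, and how one condition effect is formed from the five group coefficients.
- Keep the lavaan FIML fit as a sensitivity analysis.
- Say in the SAP that these changes do not account for variation between intervention groups.

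The cost is revised wording and a rerun with standard R tools, with no new data. TIR intervals become 11.2% (n = 49) to 12.4% (n = 45) wider, and p-values rise slightly.
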